10.7.4 Vital Signs

The vital signs results will not be listed unless any safety issue arises.

10.7.5 Exposure to Investigational Product

The formulation, period, administration site, laterality, quantity and reason of dose change/withheld (if available) of each investigational product administration will be listed for each subject. In addition a listing of the unique manufacturing lot numbers, and a listing of the subjects administered each manufacturing lot number will be provided.

10.7.6 Exposure to Concomitant Medication

All medications will be coded using the WHOdrug dictionary. Concomitant medication will not be listed or summarized unless any safety issues arise.

11. Appendices

Appendix A. Imputation Rules for Partial or Missing Stop Dates

We are using the following imputation rules:

1. For the start date
 - a. If the month is missing, impute January
 - b. If the day is missing, impute the 1
 - c. If both the month and day are missing, impute January 1.
2. For the stop date
 - a. If the month is missing, impute December
 - b. If the day is missing, impute the last day of the month
 - c. If both month and day are missing, impute December 31.
3. If the stop date is entirely missing, assume the event or medication is ongoing. If a partial or complete stop date is present and the 'ongoing' or 'continuing' box is checked, then it will be assumed that the AE or concomitant medication stopped and the stop date will be imputed, if partial.

[figure not shown]
Note: For subjects who were never treated (first dose date is missing), partial start dates will be set to the first day of the partial month. If an imputed stop date based on above rule is on or after the end of study (EOS) date, the EOS date should be used as the imputed stop date.

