7.1 Schedule of Assessments

Table 1. Schedule of Assessments

	Screening	Double-blind Treatment Period		Safety Follow-up/EOS
Days	-14 to -1	1 (\pm 3 days)	8 (\pm 3 days)	38 (\pm 7 days)^a
GENERAL & SAFETY ASSESSMENTS				
Informed consent	X			
Demographic data	X			
Registration via IVR/IWR	X			
Eligibility criteria	X			
Medical history	X			
Medication history	X			
Concomitant medications	X	X	X	
Adverse events ^b	X	X	X	
Serious adverse events ^b	X	X	X	X
Physical examination ^c	X	X	X	
Vital signs	X	X	X	
Weight	X			
Height	X			
Chest x-ray (if needed) ^d	X			
LABORATORY ASSESSMENTS				
Serum pregnancy test ^e	X			
Pregnancy test (urine) ^e		X		
Hematology profile	X			
Chemistry profile	X			
Tuberculosis testing ^f	X			
Hepatitis B and C serologies ^g	X			
DOSING				
Investigational product dispensation (etanercept)		X	X	
DISEASE ASSESSMENTS				
Physician global assessment of disease activity (VAS 0-100)	X	X	X	
SUBJECT ASSESSMENTS (Reported Outcomes)				
Injection site pain (VAS 0-100)		X	X	

Footnotes defined on next page.

EOS = end-of-study, IVR = interactive voice response, IWR = interactive web response, PPD = purified protein derivative, TNF = tumor necrosis factor, VAS = Visual Analog Scale

^a Thirty days (+ 7 days) after their last dose of etanercept, subjects will be contacted by phone by the study staff to follow-up on any continuing serious adverse events and inquire about the emergence of any new serious adverse events.

^b Adverse events and serious adverse events are collected from signing the informed consent form. Adverse device effects are included in the collection of adverse events. Adverse events are collected through the end of treatment period.

^c A full physical examination will be completed at the screening visit. Subsequent physical examinations will be conducted per standard of care to monitor for any changes.

^d Only for subjects with a positive tuberculosis test (ie, positive PPD or positive or indeterminate Quantiferon).

^e For all females, unless at least 2 years postmenopausal or postmenopausal status has been confirmed or history of hysterectomy, bilateral salpingectomy, or bilateral oophorectomy.

^f Subjects will receive either a PPD test or Quantiferon test at screening. National guidelines should be followed for appropriate tuberculosis screening in the setting of anti-TNF therapy.

^g Subjects positive for hepatitis B core antibody may require additional testing for hepatitis B DNA by polymerase chain reaction.

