9.2 Safety Event Reporting Procedures

9.2.1 Adverse Events

9.2.1.1 Reporting Procedures for Adverse Events That Do Not Meet Serious Criteria

The investigator is responsible for ensuring that all adverse events observed by the investigator or reported by the subject that occur after signing of the informed consent form through the end of treatment period are reported using the Event CRF.

The investigator must assign the following adverse event attributes:

- Adverse event diagnosis or syndrome(s), if known (if not known, signs or symptoms),
- Dates of onset and resolution (if resolved),
- Severity (and/or toxicity per protocol),
- Assessment of relatedness to etanercept and SureClick device, study procedures/study activities, and
- Action taken.

The adverse event grading scale used will be the Common Toxicity Criteria. The grading scale used in this study is described in [Appendix A](#). **If the severity of an adverse event changes from the date of onset to the date of resolution, record as a single event with the worst severity on the Event CRF.**

The investigator must assess whether the adverse event is possibly related to the etanercept and SureClick device. This relationship is indicated by a “yes” or “no” response to the question: Is there a reasonable possibility that the event may have been caused by the etanercept and SureClick device?

The investigator is responsible for reviewing laboratory test results and determining whether an abnormal value in an individual study subject represents a clinically significant change from the subject's baseline values. In general, abnormal laboratory findings without clinical significance (based on the investigator's judgment) are not to be recorded as adverse events. However, laboratory value changes that require treatment or adjustment in current therapy are considered adverse events. Where applicable, clinical sequelae (not the laboratory abnormality) are to be recorded as the adverse event.

The Investigator is expected to follow reported adverse events until stabilization or reversibility.

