12.3 Study Monitoring and Data Collection

The Amgen representative(s) and regulatory authority inspectors are responsible for contacting and visiting the investigator for the purpose of inspecting the facilities and, upon request, inspecting the various records of the clinical study (eg, CRFs and other pertinent data) provided that subject confidentiality is respected.

The Clinical Monitor is responsible for verifying the CRFs at regular intervals throughout the study to verify adherence to the protocol; completeness, accuracy, and consistency of the data; and adherence to local regulations on the conduct of clinical research. The Clinical Monitor is to have access to subject medical records and other study-related records needed to verify the entries on the CRFs.

The investigator agrees to cooperate with the Clinical Monitor to ensure that any problems detected in the course of these monitoring visits, including delays in completing CRFs, are resolved.

In accordance with ICH GCP and the sponsor's audit plans, this study may be selected for audit by representatives from Amgen's Global Research & Development Compliance and Audit function (or designees). Inspection of site facilities (eg, pharmacy, protocol-required therapy storage areas, laboratories) and review of study-related records will occur to evaluate the study conduct and compliance with the protocol, ICH GCP, and applicable regulatory requirements.

Data capture for this study is planned to be electronic:

- All source documentation supporting entries into the CRFs must be maintained and readily available.
- Updates to CRFs will be automatically documented through the software's "audit trail".
- To ensure the quality of clinical data across all subjects and sites, a clinical data management review is performed on subject data received at Amgen. During this review, subject data are checked for consistency, omissions, and any apparent discrepancies. In addition, the data are reviewed for adherence to the protocol and GCP. To resolve any questions arising from the clinical data management review process, data queries are created in the EDC system database for site resolution and subsequently closed by the EDC system or by an Amgen reviewer.

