A treatment-emergent adverse event is any adverse event that begins or worsens after the initial dose of investigational product and before the end of study. The severity of each adverse event will be graded using the CTCAE version 4.0 criteria, to be consistent with the version used for all etanercept studies. Adverse events will be coded using MedDRA (version 19.0 or later).

7. Analysis Subsets

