9.3 Handling of Missing and Incomplete Data

The following imputation for missing or incomplete data will be performed if required: Incomplete dates for adverse event and concomitant medication will be imputed as described in [Appendix A](#).

Subjects who drop out after the first injection will not be replaced by new subjects.

These subjects will be included in the safety analysis set, but not in the primary analysis set.

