10.7 Safety Analyses

10.7.1 Adverse Events and Disease Related Events

The Medical Dictionary for Regulatory Activities (MedDRA) version 19.0 or later will be used to code all events categorized as adverse events (AEs) to a system organ class and a preferred term. The severity of each adverse event will be graded using CTCAE version 4.0 criteria.

The subject incidence of AEs will be summarized for all treatment-emergent AEs, serious AEs, AEs leading to withdrawal of investigational product, fatal AEs.

Subject incidence of all treatment-emergent AEs, serious AEs, AEs leading to withdrawal of investigational product, and fatal AEs will be tabulated by system organ class and preferred term in descending order of frequency.

Summaries of treatment-emergent and serious adverse events will be tabulated by system organ class, preferred term, and grade in descending order of frequency.

Adverse events (such as injection site reactions) occurring during different periods of the treatment may be examined to evaluate the safety and tolerability of a current formulation versus the modified formulation of etanercept.

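### SAP Appendix A dates an adverse event with a missing start day to the 1st of the month without reference to first dose, so most such post-dose events would be dated pre-dose (minor)

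*SAP*

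**What the plan says.** SAP Section 9.3 sets the scope and points to Appendix A: "Incomplete dates for adverse event and concomitant medication will be imputed as described in". That appendix is titled for stop dates, but its rule 1 governs start dates. For a missing day it says "If the day is missing, impute the 1". A missing month becomes January, and a missing day and month become January 1. None of these visible rules mentions first dose.

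First dose appears once in the appendix, in the Note, which again uses the start of the known month: "For subjects who were never treated (first dose date is missing), partial start dates will be set to the first day".

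SAP Section 6 defines a treatment-emergent event as one that "begins or worsens after the initial dose of investigational product and before the end of study". SAP Section 10.7.1 then sets out the MedDRA-coded tables: "Subject incidence of all treatment-emergent AEs, serious AEs, AEs leading to withdrawal of investigational product, and fatal AEs will be tabulated".

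Protocol Table 1, footnote b, has adverse events collected from consent, and closes the window for non-serious events: "Adverse events are collected through the end of treatment period". Protocol Section 9.1.1 promises summaries overall and by indication, treatment arm and period.

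**The concern.** Pre-dose and post-dose events sit in the same dataset, and apart from worsening, the start date is what separates them. Take a first dose on 15 June and an event that began later in June on an unrecorded day. Rule 1 dates it 1 June, 14 days before exposure (15 − 1). Judged by that date it is not treatment-emergent.

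The error runs one way. When a partial date leaves onset uncertain, the visible rule resolves it as pre-treatment, which can lower treatment-emergent counts but never raise them. Adverse events are the only safety endpoint.

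The appendix is also hard to reconcile with itself. When the day is missing, rule 1 already gives everyone the first of the month. The Note's rule for never-treated subjects then adds nothing, unless treated subjects were meant to follow a different rule tied to first dose.

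**Working it through.** The plan states no figure here, so there is none to reproduce. The check applies rule 1 to possible dates.

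**Inputs from the documents**
- Imputed start: first of the known month, or January 1 if only the year is known (SAP Appendix A).
- Day 1 is the date of first dose (Protocol Section 7.2.3).
- Second visit on day 8, ±3 days (Protocol Table 1); 2-week treatment period (Protocol Section 3.5.1).

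**Assumptions**
- First-dose dates are uniform over 365 days.
- Onset is uniform over 0 to K days after first dose, with K = 7 (day-8 visit on schedule), 10 (latest day-8 visit) or 13 (2-week period).

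**Day missing, month known.** For an onset k days after first dose, the imputed date is not before first dose in two cases:
- onset falls in the next month, which holds for 12k of the 365 dose dates;
- first dose was on the 1st, which holds for 12 of the 365.

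The two do not overlap for k up to 13. The misdated share at k is 1 − 12(k + 1)/365. Averaged over k = 0 to K it is 1 − 12(K/2 + 1)/365. The share with onset in the first-dose month is 1 − 12(K/2)/365.

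| K | Misdated, all post-dose onsets | Onset in first-dose month | Misdated, given that month |
|---|---|---|---|
| 7 | 1 − 54/365 = 85.2% | 1 − 42/365 = 88.5% | 96.3% |
| 10 | 1 − 72/365 = 80.3% | 1 − 60/365 = 83.6% | 96.1% |
| 13 | 1 − 90/365 = 75.3% | 1 − 78/365 = 78.6% | 95.8% |

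Enumerating every dose date and onset day gives the same values.

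**Day and month missing.** The misdated share is 1 − (K/2 + 1)/365, which gives 98.8%, 98.4% and 97.9%.

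**Subject level, K = 7.** The tables count subjects, so a subject loses treatment-emergent status only if every one of their post-dose events is misdated. Let each event lack its day independently with probability p. The documents give no p, so 1%, 5% and 10% are an assumed range.
- One event: 0.852p = 0.85%, 4.3%, 8.5%.
- Two events sharing a first-dose date: the mean squared misdated share is (269 + 12 × 140/64)/365 = 0.809. Here 269 dose dates misdate every onset, the last 7 days of each month misdate 1/8 to 7/8 of onsets, and the 1st misdates none. Status is lost in 0.809p² = 0.008%, 0.20%, 0.81%.

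A single preferred-term row usually behaves like the one-event case. If all 112 subjects had exactly one event, the one-event rates would correspond to about 1.0, 4.8 and 9.5 subjects.

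**After the fix.** The later of first-dose date and first of the known month cannot precede first dose. In the enumeration, 0 of 2,920 (K = 7) and 0 of 5,110 (K = 13) post-dose events are dated pre-dose.

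**Price of the fix.** A day-missing screening event with onset 1 to 14 days before first dose (mean 7.5) falls in the first-dose month in 1 − 12 × 7.5/365 = 75.3% of cases.

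**The case against.** **The rule may exist but not be visible.** A reader might infer that the SAP has no first-dose rule for treated subjects. The documents do not establish that. In the text read here an unreproduced figure sits directly before the Note, the Appendix C code is redacted, and the Note itself points to such a rule. Against this, rules 1 to 3 run without a visible gap, and similar figure markers stand elsewhere with no obvious loss. The visible rule still gives a wrong date and conflicts with the Note, so a request to reconcile them stands and a charge of omission does not.

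**The loss of events is not a stated step.** A reader might also infer that the SAP removes these events from its tables. No visible text says that the treatment-emergent flag uses the imputed date, and an event captured as worsening after dosing would still qualify. This objection stands: the loss is conditional on how the flag is derived.

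**Partial dates should be few.** Onset date is a required attribute (Protocol Section 9.2.1.1). At the sponsor's data review "subject data are checked for consistency, omissions, and any apparent discrepancies", and queries follow (Protocol Section 12.3). Dosing is on site about a week apart, so recall is short. An event lacking both day and month is remote. This also stands: the 75% to 85% applies only once a day is missing.

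**The fix only reverses the direction of error.** The visible rule dates day-missing screening events correctly as pre-dose, while the replacement could count some as treatment-emergent. That is true and is a real cost. For a safety table, overcounting is the more cautious error.

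**Conclusion.** Minor, and worth a cheap change. As visible, rule 1 dates a day-missing event that began after dosing in the first-dose month before exposure, unless first dose fell on the 1st. Given a missing day, about 75% to 85% of post-dose events in the 8- to 14-day window are affected. This rests on uniform first-dose dates and onsets. The effect on the tables rests further on the flag using the imputed date, and on a frequency of partial dates that the documents do not give.

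Two stronger conclusions are not supported:
- **Bias between formulations.** The rule does not depend on formulation, allocation to sequence is 1:1, and the primary VAS endpoint does not use these dates.
- **Serious events disappearing.** Serious, fatal and withdrawal events have their own tabulations, and the contingency form for serious events has a separate box for onset before first dose. Fully dated events are untouched.

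**What to change.** In SAP Appendix A, reconcile rule 1 with the Note and state whether the treatment-emergent flag uses imputed dates. Suggested content:

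- **Treated subjects.** When the known parts of the start date are compatible with onset on or after first dose, and the stop date does not show earlier onset, impute the later of the first-dose date and the first day of the known period.
- **Flag.** Count a start imputed to the first-dose date as treatment-emergent. This must be said because the definition requires onset after the initial dose.
- **Period and formulation.** Assign them where the known month or the stop date settles the matter. With doses on 28 June and 5 July, for example, an event that stopped on 3 July belongs to the first period, whereas one known only to have begun in July, with no informative stop date, is unsettled. Count unsettled events in the overall table and show them in a separate *period not determinable* row in the by-period and by-formulation summaries, so that they keep a place in the summaries promised in Protocol Section 9.1.1.
- **Unchanged.** Keep the first-of-month rule for never-treated subjects and for concomitant medications.

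The cost is a few sentences and a small programming change. The downside is that some day-missing screening events could be counted as treatment-emergent unless the stop date shows otherwise; about 75% of those starting 1 to 14 days before first dose fall in the first-dose month.

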Appendix B. Visual Analog Scale

Subject Injection Site Pain Perception Assessment

To be evaluated immediately following injection (i.e., within 30 seconds)

[figure not shown]
Place a single vertical line  on the scale below to indicate
the severity of your pain at the injection site during and after your most recent injection.

Evaluación de la percepción del dolor en el lugar de la inyección según el/la paciente

Para ser evaluado inmediatamente después de la inyección (es decir, dentro de los 30 segundos)

Ponga una sola raya vertical  en la siguiente escala para indicar
la intensidad de su dolor en el lugar de la inyección durante y después de su última inyección.

Appendix C. Code Fragment

CCI
